### 5.2 SECONDARY OUTCOME MEASURES

1. Mean Change in Social Interaction Anxiety Scale (SIAS) Score (Both Cohorts) [Time Frame: up to 6 months]

The Social Interaction Anxiety Scale (SIAS) is a 20 item scale. Answers are on a 4 point scale starting at 0 with options "none at all", "slightly", "moderately", "very", and "extremely". Possible scores range from 0 to 80. Higher scores reflect higher levels of social anxiety. Scoring a 43 or higher may indicate a diagnosis of social anxiety, and scores between 34 and 42 may indicate social phobia(s). The SIAS is administered in both cohort 1 (Baseline, Mid-treatment, Post-treatment, up to 3 months) and cohort 2 (Baseline, Mid-treatment, Post-treatment, up to 6 months).

2. Mean Change in Psychological Wellbeing Scale Short Form - Total Score (Both Cohorts) [Time Frame: up to 6 months]

The Psychological Wellbeing Scale (Short Form) is an 18 item scale. Answers are on a 6 point scale with options "strongly disagree", "moderately disagree", "slightly disagree", "slightly agree", "moderately agree", and "strongly agree". Possible scores range from 18 to 108. Higher scores reflect higher levels of psychological wellbeing. The Psychological Wellbeing Scale is administered in both cohort 1 (Baseline, Mid-treatment, Post-treatment, up to 3 months) and cohort 2 (Baseline, Mid-treatment, Post-treatment, up to 6 months).

### **5.3 TERTIARY/EXPLORATORY OUTCOME MEASURES**

1. Mean Change in Medical Outcomes Study (MOS) Social Support Survey - Emotional/Informational Support Subscale Score (Both Cohorts) [Time Frame: up to 6 months]

The MOS Social Support Survey - Emotional/informational support subscale is an 8 item subscale. Answers are on a 5 point scale with options "none of the time", "a little of the time", "some of the time", "most of the time", and "all of the time". Possible scores range from 8 to 40. Higher scores reflect higher feelings of emotional and informational social support (more perceived emotional and informational social support). The MOS Social Support Survey - Emotional/informational support subscale is administered in both cohort 1 (Baseline, Mid-treatment, Post-treatment, up to 3 months) and cohort 2 (Baseline, Mid-treatment, Post-treatment, up to 6 months).

2. Mean Change in Medical Outcomes Study (MOS) Social Support Survey - Tangible Support Subscale Score (Both Cohorts) [Time Frame: up to 6 months]

The MOS Social Support Survey - Tangible support subscale is a 4 item subscale. Answers are on a 5 point scale with options "none of the time", "a little of the time", "some of the time", "most of the time", and "all of the time". Possible scores range from 4 to 20. Higher scores reflect higher feelings of tangible social support (more perceived tangible social support). The MOS Social Support Survey - Tangible support subscale is administered in both cohort 1 (Baseline, Mid-treatment, Post-treatment, up to 3 months) and cohort 2 (Baseline, Mid-treatment, Post-treatment, up to 6 months).

3. Mean Change in Medical Outcomes Study (MOS) Social Support Survey - Affectionate Support Subscale Score (Both Cohorts) [Time Frame: up to 6 months]

The MOS Social Support Survey - Affectionate support subscale is a 3 item subscale. Answers are on a 5 point scale with options "none of the time", "a little of the time", "some of the time", "most of the time", and "all of the time". Possible scores range from 3 to 15. Higher scores reflect higher feelings of affectionate social support (more perceived affectionate social support). The MOS Social Support Survey - Affectionate support subscale is administered in both cohort 1 (Baseline, Mid-treatment, Post-treatment, up to 3 months) and cohort 2 (Baseline, Mid-treatment, Post-treatment, up to 6 months).

3. Mean Change in Medical Outcomes Study (MOS) Social Support Survey - Positive Social Interaction Subscale Score (Both Cohorts) [Time Frame: up to 6 months]

The MOS Social Support Survey - Positive social interaction subscale is a 3 item subscale. Answers are on a 5 point scale with options "none of the time", "a little of the time", "some of the time", "most of the time", and "all of the time". Possible scores range from 3 to 15. Higher scores reflect higher feelings of positive social interaction (more perceived positive social interaction). The MOS Social Support Survey - Positive social interaction subscale is administered in both cohort 1 (Baseline, Mid-treatment, Post-treatment, up to 3 months) and cohort 2 (Baseline, Mid-treatment, Post-treatment, up to 6 months).

4. Mean Change in Psychological Wellbeing Scale Short Form - Environmental Mastery Subscale Score (Both Cohorts) [Time Frame: up to 6 months]

The Psychological Wellbeing Scale (Short Form) - Environmental Mastery Subscale is a 3 item scale. Answers are on a 6 point scale with options "strongly disagree", "moderately disagree", "slightly disagree", "slightly agree", "moderately agree", and "strongly agree". Possible scores range from 3 to 18. Higher scores reflect higher levels of environmental mastery. The MOS Social Support Survey - Environmental Mastery subscale is administered in both cohort 1 (Baseline, Mid-treatment, Post-treatment, up to 3 months) and cohort 2 (Baseline, Mid-treatment, Post-treatment, up to 6 months).

5. Mean Change in Psychological Wellbeing Scale Short Form - Personal Growth Subscale Score (Both Cohorts) [Time Frame: up to 6 months]

The Psychological Wellbeing Scale (Short Form) - Personal Growth subscale is a 3 item scale. Answers are on a 6 point scale with options "strongly disagree", "moderately disagree", "slightly disagree", "slightly agree", "moderately agree", and "strongly agree". Possible scores range from 3 to 18. Higher scores reflect higher levels of personal growth. The Psychological Wellbeing Scale - Personal Growth subscale is administered in both cohort 1 (Baseline, Mid-treatment, Post-treatment, up to 3 months) and cohort 2 (Baseline, Mid-treatment, Post-treatment, up to 6 months).

6. Mean Change in Psychological Wellbeing Scale Short Form - Self-Acceptance Subscale Score (Both Cohorts) [Time Frame: up to 6 months]

The Psychological Wellbeing Scale (Short Form) - Self-Acceptance subscale is a 3 item scale. Answers are on a 6 point scale with options "strongly disagree", "moderately disagree", "slightly disagree", "slightly agree", "moderately agree", and "strongly agree". Possible scores range from 3 to 18. Higher scores reflect higher feelings of self-acceptance. The Psychological Wellbeing Scale - Self-Acceptance subscale is administered in both cohort 1 (Baseline, Mid-treatment, Post-treatment, up to 3 months) and cohort 2 (Baseline, Mid-treatment, Post-treatment, up to 6 months).

7. Mean Change in Psychological Wellbeing Scale Short Form - Autonomy Subscale Score (Both Cohorts) [Time Frame: up to 6 months]

The Psychological Wellbeing Scale (Short Form) - Autonomy Subscale is a 3 item scale. Answers are on a 6 point scale with options "strongly disagree", "moderately disagree", "slightly disagree", "slightly agree", "moderately agree", and "strongly agree". Possible scores range from 3 to 18. Higher scores reflect higher levels of autonomy. The Psychological Wellbeing Scale - Autonomy subscale is administered in both cohort 1 (Baseline, Mid-treatment, Post-treatment, up to 3 months) and cohort 2 (Baseline, Mid-treatment, Post-treatment, up to 6 months).

8. Mean Change in Psychological Wellbeing Scale Short Form - Positive Relationships Subscale Score (Both Cohorts) [Time Frame: up to 6 months]

The Psychological Wellbeing Scale (Short Form) - Positive Relationships subscale is a 3 item scale. Answers are on a 6 point scale with options "strongly disagree", "moderately disagree", "slightly disagree", "slightly agree", "moderately agree", and "strongly agree". Possible scores range from 3 to 18. Higher scores reflect higher levels of positive relationships. The Psychological Wellbeing Scale - Positive Relationships subscale is administered in both cohort 1 (Baseline, Mid-treatment, Post-treatment, up to 3 months) and cohort 2 (Baseline, Mid-treatment, Post-treatment, up to 6 months).

9. Mean Change in Psychological Wellbeing Scale Short Form - Purpose in Life Subscale Score (Both Cohorts) [Time Frame: up to 6 months]

The Psychological Wellbeing Scale (Short Form) - Purpose in Life subscale is a 3 item scale. Answers are on a 6 point scale with options "strongly disagree", "moderately disagree", "slightly disagree", "slightly agree", "moderately agree", and "strongly agree". Possible scores range from 3 to 18. Higher scores reflect higher feelings of purpose in life. The Psychological Wellbeing Scale - Purpose in Life subscale is administered in both cohort 1 (Baseline, Mid-treatment, Post-treatment, up to 3 months) and cohort 2 (Baseline, Mid-treatment, Post-treatment, up to 6 months).

10. Qualitative Summaries of Participant Experience in Post-Treatment Feedback (Both Cohorts) [Time Frame: up to 6 months]

This qualitative data will be collected post-treatment from clients and clinicians. Focus groups and individual interviews will discuss usage of the platform and any feedback participants may have. Feedback from participants will be summarized to include common themes regarding likes and dislikes of the platform, implementation within the clinical setting, and participant ideas for future directions. Feedback is elicited at post-treatment in both cohort 1 (Month 3) and cohort 2 (Month 6).

11. Quantitative Summaries of Participant Experience in Post-Treatment Feedback (Both Cohorts)  
[Time Frame: up to 6 months]

This quantitative data will be collected post-treatment from clients and clinicians. Feedback forms will prompt participants to answer questions regarding their experience with the platform on a scale of 1 to 5, with higher scores reflecting a more positive experience. Frequency counts will be included here. Feedback is elicited at post-treatment in both cohort 1 (Month 3) and cohort 2 (Month 6).

12. Mean Change in Questionnaire about the Process of Recovery - Total Score (Cohort 2 Only) [Time Frame: up to 6 months]

The Questionnaire about the Process of Recovery (QPR) - Total Score is a 15-item scale. Answers are rated on a 5-point scale with options "disagree strongly", "disagree", "neither agree nor disagree", "agree", and "agree strongly". Possible scores range from 0 to 60. Higher scores are indicative of recovery. The QPR is administered in only cohort 2 (Baseline, Mid-treatment, Post-treatment, up to 6 months).

13. Mean Change in Modified Colorado Symptom Index - Total Score (Cohort 2 Only) [Time Frame: up to 6 months]

The Modified Colorado Symptom Index - Total Score is a 14-item scale. Answers are rated on a 4-point scale with options "not at all", "once during the month", "several times during the month", "several times a week", and "at least every day". Possible scores range from 0 to 56. Higher scores indicate greater emotional distress. The Modified Colorado Symptom Index is administered in only cohort 2 (Baseline, Mid-treatment, Post-treatment, up to 6 months).

14. Mean Change in Social Anxiety Scale for Social Media Users - Total Score (Cohort 2 Only) [Time Frame: up to 6 months]

The Social Anxiety Scale for Social Media Users (SAS-SMU) - Total Score is a 21-item scale. Answers are rated on a 5-point scale with options "never", "rarely", "sometimes", "often", and "always". Possible scores range from 21 to 105. Higher scores reflect greater anxiety related to social media usage. The SAS-SMU is administered in only cohort 2 (Baseline, Mid-treatment, Post-treatment, up to 6 months).

15. Mean Change in Social Anxiety Scale for Social Media Users - Shared Content Anxiety Subscale Score (Cohort 2 Only) [Time Frame: up to 6 months]

The Social Anxiety Scale for Social Media Users (SAS-SMU) - Shared Content Anxiety subscale is a 7-item scale. Answers are rated on a 5-point scale with options "never", "rarely", "sometimes", "often", and "always". Possible scores range from 7 to 35. Higher scores reflect greater anxiety related to sharing or creating content on social media. The SAS-SMU - Shared

Content Anxiety subscale is administered in only cohort 2 (Baseline, Mid-treatment, Post-treatment, up to 6 months).

16. Mean Change in Social Anxiety Scale for Social Media Users - Privacy Concern Anxiety Subscale Score (Cohort 2 Only) [Time Frame: up to 6 months]

The Social Anxiety Scale for Social Media Users (SAS-SMU) - Privacy Concern Anxiety subscale is a 5-item scale. Answers are rated on a 5-point scale with options "never", "rarely", "sometimes", "often", and "always". Possible scores range from 5 to 25. Higher scores reflect greater anxiety related to privacy concerns on social media. The SAS-SMU - Privacy Concern Anxiety subscale is administered in only cohort 2 (Baseline, Mid-treatment, Post-treatment, up to 6 months).

17. Mean Change in Social Anxiety Scale for Social Media Users - Interaction Anxiety Subscale Score (Cohort 2 Only) [Time Frame: up to 6 months]

The Social Anxiety Scale for Social Media Users (SAS-SMU) - Interaction Anxiety subscale is a 6-item scale. Answers are rated on a 5-point scale with options "never", "rarely", "sometimes", "often", and "always". Possible scores range from 6 to 30. Higher scores reflect greater anxiety related to social interactions over social media. The SAS-SMU - Interaction Anxiety subscale is administered in only cohort 2 (Baseline, Mid-treatment, Post-treatment, up to 6 months).

18. Mean Change in Social Anxiety Scale for Social Media Users - Self-Evaluation Anxiety Subscale Score (Cohort 2 Only) [Time Frame: up to 6 months]

The Social Anxiety Scale for Social Media Users (SAS-SMU) - Self-Evaluation Anxiety subscale is a 3-item scale. Answers are rated on a 5-point scale with options "never", "rarely", "sometimes", "often", and "always". Possible scores range from 3 to 15. Higher scores reflect greater anxiety related to negative self-evaluation. The SAS-SMU - Self-Evaluation Anxiety subscale is administered in only cohort 2 (Baseline, Mid-treatment, Post-treatment, up to 6 months).

19. Mean Change in Perceived Autonomy Support Scale - Total Score (Both Cohorts) [Time Frame: up to 20 weeks]

The Perceived Autonomy Support Scale - Total Score is a 6-item scale. Answers are on a 7-point scale with options "strongly disagree", "moderately disagree", "slightly disagree", "neutral", "slightly agree", "moderately agree", and "strongly agree". Possible scores range from 6 to 42. Higher scores reflect greater perceived autonomy support. The Perceived Autonomy Support Scale is administered in both cohort 1 (Mid-treatment, Post-treatment, up to 6 weeks) and cohort 2 (1.5 Months, Mid-treatment, 4.5 Months, Post-treatment, up to 20 weeks).

20. Mean Change in Working Alliance Inventory for Guided Internet Interventions - Total Score (Both Cohorts) [Time Frame: up to 20 weeks]

The Working Alliance Inventory for Guided Internet Interventions (WAI-I) - Total Score is a 12-item scale. Answers are on a 5-point scale with options "seldom", "sometimes", "fairly often", "very often", and "always". Possible scores range from 12 to 60 (summed) or 1 to 5 (averaged). Higher scores reflect greater therapeutic alliance. The WAI-I is administered in both cohort 1 (Mid-treatment, Post-treatment, up to 6 weeks) and cohort 2 (1.5 Months, Mid-treatment, 4.5 Months, Post-treatment, up to 20 weeks).

**21. Mean Change in Working Alliance Inventory for Guided Internet Interventions - Bond Subscale Score (Both Cohorts) [Time Frame: up to 20 weeks]**

The Working Alliance Inventory for Guided Internet Interventions - Bond subscale score is a 4-item scale. Answers are on a 5-point scale with options "seldom", "sometimes", "fairly often", "very often", and "always". Possible scores range from 4 to 20 (summed) or 1 to 5 (averaged). Higher scores reflect greater bond with a clinician. The WAI-I - Bond subscale is administered in both cohort 1 (Mid-treatment, Post-treatment, up to 6 weeks) and cohort 2 (1.5 Months, Mid-treatment, 4.5 Months, Post-treatment, up to 20 weeks).

**22. Mean Change in Working Alliance Inventory for Guided Internet Interventions - Goal/Task Subscale Score (Both Cohorts) [Time Frame: up to 20 weeks]**

The Working Alliance Inventory for Guided Internet Interventions - Goal/Task Score is an 8-item scale. Answers are on a 5-point scale with options "seldom", "sometimes", "fairly often", "very often", and "always". Possible scores range from 8 to 40 (summed) or 1 to 5 (averaged). Higher scores reflect greater shared goals and tasks with a clinician. The WAI-I - Goal/Task subscale is administered in both cohort 1 (Mid-treatment, Post-treatment, up to 6 weeks) and cohort 2 (1.5 Months, Mid-treatment, 4.5 Months, Post-treatment, up to 20 weeks).

**23. Mean Change in Twente Engagement with E-health Technologies Scale - Total Score (Cohort 2 Only) [Time Frame: up to 6 months]**

The Twente Engagement with E-health Technologies Scale - Total Score is a 9-item scale. Answers are on a 5-point scale with options "strongly disagree", "disagree", "neutral", "agree", and "strongly agree". Possible scores range from 0 to 36. Higher scores reflect greater engagement. The Twente Engagement with E-health Technologies Scale is administered in only cohort 2 (Baseline, 1.5 Months, Mid-treatment, 4.5 Months, Post-treatment, up to 6 months).

## **5.4 POWER ANALYSIS**

We did not conduct *a priori* power calculations to determine a sample size with 80% power because this is an exploratory study and will inform future well-powered and randomized pilot trials of Horyzons in North Carolina.

## **5.5 DATA MANAGEMENT**

We will use the Research Electronic Data Capture (REDCap) system to facilitate data entry and management. We will leverage features in REDCap such as real-time data validation, built-in integrity checks, and other mechanisms for ensuring data quality (i.e., double data entry). Our team will use the DeDoose program for qualitative analysis. All analyses will be conducted by the study research coordinator ([name]) and graduate student ([name]).

## 6 RISKS AND BENEFITS

Risks for all participants. Identifying research subjects by a study number on all research documents minimizes risk of breach of confidentiality. Study documents that must contain personal information, such as the document that links study ID number to personal identifying information (necessary due to the longitudinal nature of this study) are kept in locked filing cabinets in locked rooms. Research data is kept on password-protected drives, and our computer systems are HIPAA compliant. All study staff participate in annual human subjects training that includes education about responsibilities to minimize risk that confidentiality may be breached.

Risks for clients only. Risk of anxiety, paranoia, and/or shame/embarrassment due to experiences using this online platform is minimized by completion of a Horyzons induction procedure. This will also be mitigated through the use of consistent moderating of the site as well as moderators' use of a nonjudgmental clinical attitude. The informed consent process will be completed in private spaces within the clinic/research setting or via video conferencing will be done in secure locations and on secure servers. The participant will be instructed via email or phone call before the interview to find a private location to complete the induction to the platform. All documents such as consent and feedback measure/questionnaire will be sent to the participant using a secure UNC email account. Documents will not contain confidential information.

Risks for providers only. The informed consent process will be completed in private spaces within the clinic/research setting or via video conferencing will be done in secure locations and on secure servers. Providers will be instructed via email or phone call before the focus groups to identify an appropriate location for the group discussion (i.e., private space) if held virtually rather than in person. All documents such as consent documents will be sent to providers using a secure UNC email account. Documents will not contain confidential information.

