#### **Efficacy Evaluations**

Primary outcomes (both cohorts) - The UCLA Loneliness Scale and MOS Social Support Survey (total score) will be used to assess subjective feelings of loneliness and social support.

Secondary outcomes (both cohorts) - The SIAS and short-form PWS will be used to assess subjective feelings of social anxiety and psychological wellbeing.

Tertiary/Exploratory Outcomes (both cohorts) - Quantitative and qualitative feedback collected at post-treatment and in focus groups will be used to explore feasibility and acceptability of Horyzons as a support tool in NC FEP clinics. Subscales from the MOS Social Support Survey and the short-form PWS as well as total scores from the WAI-I and Perceived Autonomy Support Scale may be explored in data analysis. Among the second cohort only, other scales/subscales such as the Questionnaire about the Process of Recovery, Social Anxiety Scale for Social Media Users, Modified

---

|  |   |
|--|---|
|  | Colorado Symptom Index, and Twente Engagement with eHealth Technologies Scale may be explored in data analysis.   |
| Safety Evaluations              | A safety plan for Horyzons was developed before participants joined the Horyzons digital platform by PI [name] and study coordinator [name]. All safety measures were approved by the director of each NC FEP clinic.   |
| Statistical And Analytic Plan   | Analyses will primarily be descriptive in nature. We will calculate means, standard deviations, and effect sizes of the primary outcomes (loneliness, social support) and secondary outcomes (social anxiety, psychological wellbeing).   |
| DATA AND SAFETY MONITORING PLAN | Privacy and online safety will be managed in accordance with the 'Online social networking' guidelines published by 'Cybersmart', a national cybersafety and cybersecurity education program managed by the Australian Communications and Media Authority (ACMA). Online safety will be monitored by Horyzons moderators (clinicians involved in the project, peer support specialists, graduate students in the Department of Psychology and Neuroscience) with supervision from the Principal Investigator. [name] will function as the Project Medical Officer. |

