## **2 RESEARCH DESIGN AND METHODS**

### **2.1 OVERVIEW**

Participants (clients) will be given access to Horyzons (which is considered a “non significant risk” medical device and is described below) from their date of enrollment up to 3 months in the first cohort (enrolling January 2021) and up to 6 months in the second cohort (enrolling February 2022). Horyzons will be monitored daily (two hours per weekday & one hour per weekend day) by trained peer support specialists, master's level clinicians, [name] (PI), and/or graduate students in the Department of Psychology and Neuroscience at UNC. In an effort to facilitate and monitor engagement, a protocol is in place that directs moderators to contact participants via text message and/or email if an he/she/they have not logged onto the platform for two weeks, and via telephone if a participant remains inactive for an additional two weeks. The principal investigator, [name], will lead weekly supervision calls to ensure appropriate care and support of clients involved in this project, to discuss case conceptualization and suggestions for engaging clients in the platform, as well as to monitor any potential safety concerns.

Overview of Horyzons. Horyzons is an online social media platform that integrates: i) peer-to-peer on-line social networking; ii) individually tailored interactive psychosocial interventions; and (iii) expert moderation.

*Peer-to-peer online social networking (the “Community”).* The ‘community’ page includes a web feed where clients and moderators can post comments, information, upload pictures and videos, and ‘like’ different content. Moreover, the system includes a ‘wall’ function displaying the activity of individual users, and a ‘network’ (similar to a ‘friends’ function). The open trial also incorporates the participation of peer support specialists. Peer supports are individuals with lived experience of severe mental illness who are familiar with the Horyzons platform and affiliated with one of the first episode clinics in North Carolina

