Safe and informed orientation to the system will be a priority for the research team. Peer support specialists, clinicians, and/or a graduate student in the Department of Psychology and Neuroscience at UNC-CH will meet with each participant to provide them with login information, help set up their account and orient them to the Horyzons system, including details of the terms of use. All users of Horyzons will be asked to nominate an emergency contact person, such as a close family member. The terms of use explain to users that information passed onto moderators or communicated within the system that may indicate concerns regarding their wellbeing may be communicated with their treating team or private practitioner. Hard copies of 'Horyzons Terms of Use' will be provided to users which will be made available online and in printed form. Participants will be required to sign the hard copy as well as accepting the terms of use on entry into the system. The system also includes a "report function" which enables users at any time to indicate to the moderator a concern about any material posted by a user, including concern about potential abuse or concerns about the well being of another participant. The moderator will assess the basis of the report and respond accordingly, which can include the removal of the material or deactivation of an account.

In addition, users will be able to "switch off" their profile and hide all of their existing comments on the system should they become concerned about their privacy during their course of participation. The limits of the moderator to respond (e.g., in a timely manner to emergencies) will also be fully explained. In order to protect the privacy of users who discontinue using the system, any accounts that have not been activated for one month may be deactivated following a follow-up telephone call from the moderator. Specifically, our disengagement protocol is such that a participant will receive an email/call/text message if they have not logged onto the platform for two weeks. If another two weeks pass, we will call this person to check in about any potential issues or concerns. If participants do not comply with the guidelines for safe use of Horyzons (e.g., discriminatory comments towards other users) they will be excluded from the system.

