## 7 SAFETY MANAGEMENT

### 7.1 ADVERSE EVENTS

Client activity on the platform will be monitored daily by the online moderators and PSS. Signs of potential clinical deterioration will be reported to the client's treatment team. It is highly unlikely that clinical deterioration will be attributable to the Horyzons system. However, in the event that this becomes evident (e.g., a participant has clearly communicated that they have incorporated aspects of the Horyzons system into their delusional beliefs) the moderator will communicate this information to the clinical treatment team and/or the principal investigator. The principal investigator will inform the IRB of any concerns regarding adverse events associated with involvement in Horyzons.

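### The platform-related harms the protocol names (anxiety, paranoia, shame) are not systematically asked about or counted, and mean changes can hide clients who worsen

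*Combined protocol and SAP*

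**What the plan says.** Section 6, on risks for clients only, states: "Risk of anxiety, paranoia, and/or shame/embarrassment due to experiences using this online platform is minimized by completion of a Horyzons induction procedure". It adds moderation and a non-judgmental attitude as further mitigation. Neither Section 6 nor 6.1 names a measure of these three harms. The synopsis and Section 3 both list evaluating the safety and privacy arrangements among the study's objectives.

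Section 7.1 opens the handling of adverse events with "Client activity on the platform will be monitored daily by the online moderators and PSS". For clients who stop using the site, Section 6.1 says that "a participant will receive an email/call/text message if they have not logged onto the platform for two weeks" and then "If another two weeks pass, we will call this person to check in about any potential issues or concerns". Section 2.1 repeats the second step: "via telephone if a participant remains inactive for an additional two weeks".

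On outcomes, SIAS is given in both cohorts and is defined as a mean change. Section 5.2 notes that "Scoring a 43 or higher may indicate a diagnosis of social anxiety", but no analysis uses that cut-off. Section 5.3 says "The Modified Colorado Symptom Index is administered in only cohort 2", and the Social Anxiety Scale for Social Media Users is likewise limited to cohort 2. The statistical row of the synopsis reads "We will calculate means, standard deviations, and effect sizes of the primary outcomes", and continues with the secondary outcomes.

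**The concern.** A protocol that names specific harms and makes safety an objective would be expected to say how those harms are elicited, counted and reported. This one gives mitigation and surveillance, but no question put to every client and no tabulation. Its scale outcomes are group averages, in which improvement in most clients can cancel worsening in a few.

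Section 5.4 says the study is meant to inform later randomized trials. If it reports no change in anxiety and few or no platform-related events, those trials may take that as evidence of safety. It could equally reflect that these harms were never systematically asked about.

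**Working it through.** The documents give no harm rate, worsening threshold, standard deviation or power calculation, so there is no figure of the plan's own to reproduce. The check has two parts: coverage read from the text, and illustrations on assumed values.

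**1. Does any route ask every client about the three harms, or count them?**

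- *Scheduled visits (4.1.2 to 4.2.3).* The baseline, mid-treatment, post-treatment and (cohort 2) 1.5- and 4.5-month procedures list scales, and at post-treatment a feedback survey and interview. None lists an adverse-event question.
- *Serious adverse events (7.2).* These are to be evaluated at each clinic visit, but only against the serious criteria. Section 9 calls the study fully virtual, so what counts as a clinic visit needs reconciling.
- *Keyword blocking (6.1).* The list covers self-harm, violence and drug terms. It has none for paranoia, anxiety or shame.
- *In-platform symptom monitoring (6.1) and module review (2.1).* These operate within the site and so presumably depend on use. Neither is tied to an outcome.
- *Inactivity contacts (2.1, 6.1).* The trigger is absence of log-in, so a client who logs in without posting does not set it off. Nothing says that the findings of the call are recorded or reported.
- *Feedback (2.1; 5.3, items 10 and 11).* The form is described as optional, and its scores run from 1 to 5 towards a more positive experience. Interviews are summarised by common themes, so a problem affecting few clients may drop out.
- *Outcome list (5.1 to 5.3).* There are 2 primary, 2 secondary and 24 exploratory outcomes (numbered to 23, with number 3 used twice): 2 + 2 + 24 = 28. None is an adverse-event count or a count of clients who worsen, and none is specific to paranoia or shame.

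**2. How late is the telephone check-in?** It comes after four weeks without log-in, against follow-up of 12 and 26 weeks (Section 2.1): 4/12 = 33% of cohort 1's period and 4/26 = 15% of cohort 2's. The first contact, at two weeks, is at 2/12 = 17% and 2/26 = 8%.

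**3. Can a mean hide worsening?** Client numbers are 25 and 37 from the synopsis (Section 2.2 allows up to 30 and 60). The SIAS changes are assumed. Higher is worse.

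- Cohort 2, 6 clients worsen by 15 and 31 improve by 3:
  - mean = (6 × 15 − 31 × 3)/37 = (90 − 93)/37 = −0.08
  - SD = √[(6 × 15.08² + 31 × 2.92²)/36] = 6.7
  - effect size = −0.08/6.7 = −0.01, with 6/37 = 16% worse
- Some clients worsen by 10 and the rest improve by 5, so mean = [10k − 5(n − k)]/n:

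| n | k worse | mean change |
|---|---|---|
| 25 | 2 | −3.8 |
| 25 | 5 | −2.0 |
| 25 | 8 | −0.2 |
| 37 | 4 | −3.4 |
| 37 | 7 | −2.2 |
| 37 | 11 | −0.5 |

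With about 30% of clients worse, the mean still points to improvement.

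**4. What would asking everyone show?** Assume full response and accurate reporting. The chance of at least one case is 1 − (1 − p)ⁿ. At an assumed true rate of 5% it is 72% for n = 25 and 85% for n = 37; at 10% it is 93% and 98%. If no client reported a harm, the one-sided 95% upper bound, 1 − 0.05^(1/n), would be 11.3% and 7.8%.

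**The case against.** The strongest reply is that the plan watches clients by many routes. Moderators screen risk information twice daily, including early warning signs from symptom monitoring that is separate from posts. They review individual modules, and other users can report concern about a participant. Each page carries a number for platform-related emergencies, and supervision is weekly. Clients who stop logging in are contacted and then telephoned. Every client is due a 60-minute individual interview at post-treatment, which is a direct opening for a bad experience.

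All of this stands. A reader might infer from Section 7.1 that monitoring rests only on what clients post, or that a client who goes quiet is never seen. The documents do not support either inference. What the reply does not supply is a uniform question, a record or a count.

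Three further objections have some force. The worked values are assumed, and the −3 and +15 were chosen so as to cancel; they show that masking is possible, not that it is likely. Standard deviations are planned too, though an SD does not identify who worsened. And the study is exploratory, without hypotheses, and was deemed of non-significant risk, which argues for a light remedy. It does not remove the need for one, because safety is among the objectives.

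Counting only clients who cross 43 on SIAS would also be a poor remedy. It misses a 15-point worsening from 20 to 35 or from 45 to 60, yet counts a move from 42 to 43.

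**Conclusion.** The point holds as a gap in eliciting and reporting harm. It is not an absence of monitoring. The three named harms have no scheduled question and no prespecified count, check-in findings are not said to be reported, and individual worsening is not tabulated. Cohort 1 is the less well covered, since the symptom index and the social-media anxiety scale are not given there.

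The size cannot be estimated from the documents. On the assumed values, between 16% and about 30% of clients could worsen while the SIAS mean shows essentially no change or a slight improvement. That assumes all clients are assessed; loss of those who disengage would add to the uncertainty.

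This should be changed, because it decides what the study can say about safety. It does not affect the validity of the planned descriptive summaries. It would also be too strong to read later worsening counts as harm caused by Horyzons: a single-arm study cannot establish that.

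**What to change.** 1. Beside mean change, report by cohort at mid- and post-treatment the number and proportion (n/N assessed) of clients whose SIAS worsens by at least an amount that the investigators prespecify. In cohort 2, do the same for the Modified Colorado Symptom Index. Crossing 43 on SIAS may be shown in addition, but not alone.
2. Add three fixed yes/no items to the existing mid- and post-treatment assessments, asking whether, since the last assessment, using Horyzons has made the client (a) more anxious, (b) more suspicious or paranoid, (c) ashamed or embarrassed. Report each as n/N.
3. At the existing four-week inactivity call, ask the same items and record the reason for disengaging. Report these with the number of clients reached.

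Item 1 uses data already collected and costs a few table rows. Items 2 and 3 add about a minute to contacts that already take place. The answers are self-attributed and therefore imperfect. The worsening amounts, and any clinical response to an answer, are for the investigators to set.
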